11 A serum pregnancy test will be performed on all women of childbearing potential at Screening. The sample collected for clinical chemistry analysis may be used for this purpose. A urine pregnancy test will be performed on all women of childbearing potential at Visit 2 and the End-of-Study (or Early Exit) visit. If the subject is participating in the optional imaging sub-study, the Visit 2 urine pregnancy test will be performed prior to performing the MRI. It does not need to be repeated prior to dosing.

12 HbA1c will be measured at Screening and End-of-Study (or Early Exit) visits.

13 To be collected at approximately the same time each visit, between 7-11 a.m. The clinical chemistry sample can be used for cortisol analysis, if being collected at the same visit.

14 Prior to and 2 hours after dosing. (For the 2 hour post-dose assessment a -15/+15-minute window is permitted.)

15 The ACTH stimulation test may be performed at any time of day and on any day during Screening, including at Visit 1b.

16 If the morning serum cortisol test result at Visit 6 (Week 8) is <350 nmol/L (<12.7 µg/dL) an ACTH stimulation test is to be performed at Visit 7 (Week 12). The site will be notified of this requirement in advance of the subject attending this visit.

17 For subjects whose ACTH stimulation test was abnormal at Visit 7, the test will be repeated at the End-of-Study (or Early Exit) Visit (the site will be notified of this requirement in advance of the subject attending this visit).

18 For those subjects not undergoing the ACTH stimulation test at Visit 9 (Week 24/Early Exit) if the result of the morning serum cortisol test at this visit is <350 nmol/L (<12.7 µg/dL), the site will be informed that an unscheduled visit is required to perform an ACTH stimulation test.

Notes:
ACTH=Adrenocorticotrophic hormone; AEs=Adverse events; Chem=Blood chemistry panel; Commed=Concomitant medication; ePRO=Electronic patient-reported outcome; Hem=Blood hematology panel; MDGA=Physician's Global Assessment of Arthritis; MRI=Magnetic resonance imaging; NPRS=Numerical pain rating scale; OA=Osteoarthritis; PK=Pharmacokinetic; PIgA=Patient's Global Assessment of Arthritis; SF-36=Short Form 36 questionnaire; WOMAC=Western Ontario and McMaster Universities Osteoarthritis Index.

IMAGING SUB-STUDY ADDITIONAL SCHEDULE OF EVENTS

Visit	1a Screening (Multiple days)	2 Baseline & Dosing	7	9 End-of-Study (or Early Exit Visit)	10 Imaging Follow-up
Study Week	-8 to -3	1	12	24	52

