25. Currently has or is receiving treatment for the following conditions: psychotic disorder, bipolar disorder, symptomatic depressive or anxiety disorders. Mild or well-controlled psychiatric disorders (e.g., mild depression) are permitted if the medication used is not prohibited by the protocol (see Section 8.1).
26. At Screening, a baseline serum cortisol value ≤ 138 nmol/L (≤ 5 μ g/dL) from the ACTH stimulation test, or an abnormal ACTH stimulation test result.
27. Currently has diagnosed insulin-dependent diabetes mellitus or poorly controlled non-insulin dependent diabetes mellitus (defined as a hemoglobin A1c (HbA1c) value of $\geq 8.0\%$ (64 mmol/mol) at Screening.
 - Pre-diabetics (i.e., HbA1c levels between 5.7-6.4% (39-46 mmol/mol) at Screening) and well-controlled non-insulin dependent diabetics (i.e., HbA1c levels $\leq 7.9\%$ (63 nmol/mol) at Screening) are permitted.
28. Diagnosed hepatic or renal disease, or the following laboratory values at Screening: aspartate aminotransferase (AST) or alanine aminotransferase (ALT) $> 3 \times$ upper limit of normal (ULN); bilirubin $> 2 \times$ ULN (unless isolated Gilbert's syndrome); serum creatinine $> 1.5 \times$ ULN.
29. Current malignancy of any type, or history of a malignancy within 12 months prior to Screening (other than resected basal cell carcinoma, squamous skin cell carcinoma, or resected cervical atypia or carcinoma in situ).
30. Any infection requiring IV antibiotics within 4 weeks of the Baseline Visit, or oral antibiotics within 2 weeks of the Baseline Visit.
31. Known active or quiescent systemic fungal, bacterial (including tuberculosis), viral or parasitic infections, or ocular herpes simplex.
32. Known or clinically suspected infection with human immunodeficiency virus, hepatitis B or C viruses.
33. Skin breakdown on the Index knee where the injection will take place.
34. Females who are pregnant, lactating, or who have a positive pregnancy test result at Screening or Baseline Visits.
35. Known or suspected hypersensitivity or contraindication to any of the ingredients in the investigational medicinal product, including carboxymethyl cellulose and polysorbate 80, to fluticasone propionate or any other corticosteroids (for example cortisol-related endocrinopathy), or to lidocaine (if used during IA injection procedure).
36. Known or pending disability or workers' compensation claims.
37. Previous randomization and treatment in this study.

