9.1.5.1.2 ACTH Stimulation Test

The ACTH stimulation test measures the ability of the adrenal cortex to respond to ACTH by appropriately producing cortisol. It is used to help diagnose adrenal insufficiency (AI).

The ACTH stimulation test involves the following steps (full details will be provided in the Laboratory Manual). Subjects are not required to be fasting for this test. The ACTH stimulation test may be performed at any time of day.

The procedure for the ACTH test is as follows:

- A baseline blood sample will be collected to measure serum cortisol and ACTH
 - If the ACTH stimulation test occurs on a scheduled visit where a morning serum cortisol sample is already being collected between 7 and 11 a.m., only a baseline blood sample for the measurement of ACTH is required.
- Inject the provided cosyntropin into the subject's shoulder muscle
- 30 minutes (± 5 minutes) post-injection, collect a blood sample to measure serum cortisol
- 60 minutes (± 5 minutes) post-injection, collect a blood sample to measure serum cortisol

The test will be performed in the following circumstances:

- **Visit 1a – Visit 1b** (Screening) in all subjects
 - This is to identify subjects with existing, undiagnosed AI, so they can be excluded from the study.
- If the subject's **Visit 6** (Week 8) serum cortisol is <350 nmol/L (<12.7 μ g/dL), perform the ACTH stimulation test at **Visit 7** (Week 12)
 - This is intended to identify if a subject with serum cortisol levels at the lower end of the normal range has developed asymptomatic AI in response to peak exposures of EP-104IAR.
 - If the subject's **Visit 7** (Week 12) ACTH stimulation test is abnormal, repeat the ACTH stimulation test at **Visit 9** (Week 24/End-of-Study/Early Exit Visit).
- If the subject's **Visit 9** (Week 24/End--of--Study/ Early Exit Visit) serum cortisol is <350 nmol/L (<12.7 μ g/dL), perform the ACTH stimulation test at an **Unscheduled Visit**
 - This is intended to identify if a subject with serum cortisol levels at the lower end of the normal range has developed slow developing asymptomatic AI in response to EP-104IAR administration, as it can take several weeks for AI to develop following adrenal atrophy.

- Not required if the subject has already completed an ACTH test at Visit 9 due to an earlier abnormal ACTH result.

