- If the subject's serum cortisol is ≤ 138 nmol/L (≤ 5 μ g/dL) at **any visit** after dose administration **AND** they experience signs and symptoms of AI (see Section 10.2.5), perform the ACTH stimulation test at the **next scheduled visit**.

See [Figure 2](#) below.

During Screening, sites will receive serum cortisol results from the ACTH stimulation test directly from the central safety laboratory to determine subject eligibility. At all later timepoints serum cortisol results will be received by the unblinded Medical Monitor, who will inform the site which subjects should undergo the ACTH stimulation test. ACTH stimulation test results will be reported to the unblinded Medical Monitor for review.

[figure not shown]
Criteria for evaluating if the ACTH stimulation test response is normal or abnormal are provided in the Laboratory Manual.

If the results of the ACTH stimulation test are considered to be abnormal and the subject also displays symptoms of adrenal suppression, they should be managed accordingly and may require glucocorticoid replacement therapy (e.g., with physiologic hydrocortisone). If appropriate, such subjects should be referred to an Endocrinologist (or other appropriate specialist) for further evaluation and treatment.

The ACTH stimulation test is extremely sensitive (95% sensitivity and 97% specificity); however, this translates to a false positive result in approximately 1 out of every 20 tests. The ACTH stimulation test will be repeated at the End-of-Study Visit in any subjects with an abnormal test result at Week 12.

Subjects who are diagnosed with AI following dose administration should be managed by their Endocrinologist (or other appropriate specialist) until resolution. If the subject's AI is ongoing at their final scheduled study visit, the Investigator should follow-up with the subject approximately 3 months later, with at least 1 additional contact during that 3-month period.

Figure 2 Triggers for ACTH Stimulation Testing

Note: ACTH=Adrenocorticotrophic hormone Wk=Week.

Protocol No. EP-104IAR-201 - Version 7.0
15 Aug 2022

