9.2.7 Unscheduled Visits

Unscheduled visits may be performed at the Investigator's discretion if there are safety findings of concern at scheduled visit assessments or reported by subjects between visits.

An unscheduled visit should also be performed in the following circumstances:

- **All subjects** - If the subject requires additional rescue medication between scheduled visits, they may call the site to obtain an additional bottle of rescue medication.
- **All subjects** - If at any time during the study a subject independently reports symptoms indicative of an infection in the Index knee (e.g., a red and swollen knee with moderate or large effusion, or a hot and swollen knee with a moderate or large effusion), a blood sample will be collected for hematology testing and the subject should be referred for further specialist assessment as soon as possible.
- **Subjects with abnormal ACTH stimulation test results** - If the ACTH stimulation test performed at Visit 9 (Week 24/End-of-Study/Early Exit) is abnormal (as per the unblinded Medical Monitor's assessment), the subject should be asked to return to the site for a repeat test to confirm the initial result and additional safety evaluations, as required.
- **Subjects with abnormal serum cortisol test results** – If the serum cortisol test at Visit 9 (Week 24/End-of-Study/Early Exit) is abnormal as per the unblinded Medical Monitor's assessment (and the subject did not already complete an ACTH stimulation test at that visit), the subject should be asked to return to the site to complete an ACTH stimulation test.
- **Subjects who withdraw early** – If a subject withdraws early from the study and their most recent visit serum cortisol was <350 nmol/L (<12.7 µg/dL) (as per the unblinded Medical Monitor's review) the subject should be asked to return to the site for an ACTH stimulation test and additional safety evaluations, as required.

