### 3. STATISTICAL METHODOLOGY

#### 3.1 General Principles

All collected study data will be presented in listings. All derivations and statistical analyses will be performed using SAS® software Version 9.4 (or higher) or Phoenix® WinNonlin® Version 8.3 (or higher) (Certara USA, Inc., Princeton, NJ). Prior and concomitant medications/procedures will be coded using World Health Organization (WHO) Drug Dictionary Enhanced March 1, 2021 (or most recent version prior to data base lock). Adverse events will be coded using Medical Dictionary for Regulatory Activities (MedDRA) Version 24.0 (or most recent version prior to data base lock).

Unless stated otherwise, descriptive summaries for continuous variables will include n (number of subjects with non-missing results), mean, standard deviation (SD), median,  $Q_1$ ,  $Q_3$ , minimum, and maximum. For categorical variables, n and percent will be provided. Percentages will be calculated out of the number of subjects in the given sample with a non-missing result.

The primary means of efficacy data collection will be via an electronic patient-reported outcome (ePRO) device. Subjects will be provided with a hand-held device programmed to prompt the subject to record data as required throughout the study. The primary means of non-efficacy data collection will be via the electronic case report forms (eCRFs).

Summaries presented by collection day and/or by time point will be based on scheduled assessments as planned in the protocol except for all WOMAC data (See Section 4.1). Unscheduled assessments will be presented in listings and will not be included in the analyses except for: determination of baseline as described in Section 4.3, ACTH stimulation test summaries (See Section 4.4), and for the derivation of PK parameters.

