#### ACTH Stimulation Tests

Results for ACTH stimulation tests will be summarized by frequency and percentage of positive tests, and listed for each subject.

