#### 4.4 Unscheduled Data

Except for ACTH stimulation test results as described below, data obtained from unscheduled assessments (which also includes early exit visits) will only be considered for baseline determination; otherwise, unscheduled data will not be used in summary tables or included in the analyses. All unscheduled data will be presented in the listings.

ACTH stimulation test results will be mapped via the windowing rules in the below table. When more than one result for a subject occurs within one visit window, the worst result (i.e., Fail) will be mapped to that visit.

Visit (Mapped)	Target Day	Study Day Range
Screening		<1
Week 1	Day 3	1-9
Week 2	Day 15	10-22
Week 4	Day 29	23-43
Week 8	Day 57	44-71
Week 12	Day 85	72-106
Week 18	Day 127	107-148
Week 24	Day 169	149+

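### Minor: 97% specificity means about 1 false-positive ACTH test in 33, not 1 in 20, and the SAP's percentage positive uses a selected denominator and gives no first-test or repeat counts

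*Protocol*

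**What the plan says.** **Accuracy of the test.** Protocol 9.1.5.1.2 states 95% sensitivity and 97% specificity and adds that "this translates to a false positive result in approximately 1 out of every 20 tests".

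**Who is tested.** Everyone is tested at Screening, and Exclusion Criterion 26 removes those with a low baseline cortisol "or an abnormal ACTH stimulation test result". After dosing, testing is selective (Protocol 9.1.5.1.2 and 9.2.7):

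- Week 8 cortisol below 350 nmol/L leads to a test at Week 12.
- An abnormal Week 12 test leads to a retest (Schedule of Events, footnote 17): "For subjects whose ACTH stimulation test was abnormal at Visit 7, the test will be repeated at the End-of-Study (or Early Exit) Visit".
- Visit 9 cortisol below 350 nmol/L leads to a test at an unscheduled visit. This is "Not required if the subject has already completed an ACTH test at Visit 9 due to an earlier abnormal ACTH result".
- Cortisol of 138 nmol/L or less with signs of adrenal insufficiency (AI) leads to a test at the next scheduled visit.
- Early withdrawal with a latest cortisol below 350 nmol/L leads to a return visit for a test.

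**Confirmation.** Under Protocol 9.2.7, if the Visit 9 test is abnormal, "the subject should be asked to return to the site for a repeat test to confirm the initial result".

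**Reporting.** Under SAP 3.8.4.2, ACTH results are "summarized by frequency and percentage of positive tests" and listed by subject. SAP 3.1 sets the denominator: "Percentages will be calculated out of the number of subjects in the given sample with a non-missing result". SAP 4.4 admits unscheduled ACTH results, places everything from Day 149 onward in Week 24, and says that where a window holds several results, "the worst result (i.e., Fail) will be mapped to that visit".

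**The concern.** The quoted false-positive rate does not follow from the specificity in the same sentence. It matters only as background for reading a count of abnormal tests, but it errs towards treating positives as test error.

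The reporting question has more substance. HPA-axis suppression is a systemic risk that the protocol singles out (Sections 2.1.2 and 2.2), and some effect on cortisol is expected. Cortisol also decides who is tested, so the percentage positive is taken out of a group selected after randomization by something treatment can change. It does not compare the arms as randomized. In addition, the summary does not show which positives came from a first test, which were seen again on a repeat, and which persisted from Week 12 to Week 24.

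**Working it through.** **1. The false-positive rate.** Inputs: sensitivity 0.95 and specificity 0.97 (Protocol 9.1.5.1.2).

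- The plan's figure is reproduced only by 1 − sensitivity: 1 − 0.95 = 0.05 = 1/20.
- The false-positive rate is 1 − specificity: 1 − 0.97 = 0.03 = 1/33.3.
- As a share of all tests it is 0.03 × (1 − p), where p is the AI prevalence among those tested. It cannot exceed 3%: at p = 5% it is 2.85% (1 in 35), and at p = 10% it is 2.7% (1 in 37).
- All wrong results together, 0.03(1 − p) + 0.05p, run only from 3.0% to 4.0% for p from 0 to 50%.
- The false share of *positive* results equals 5% only at p = 37.5%: 0.01875 / (0.01875 + 0.35625) = 0.05. That is not a share of tests.
- If the two figures were transposed (97% sensitivity, 95% specificity), 1 in 20 would be right. The documents cannot settle this.

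**2. Expected false positives.** The number tested is not given; Protocol 6.2 says only that it will be a large proportion of both arms. Assume 25%, 50% or 75%, with no AI.

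| Base per arm | Tested | At 3% | At 1 in 20 |
|---|---|---|---|
| 150 (all dosed) | 38 / 75 / 113 | 1.1 / 2.3 / 3.4 | 1.9 / 3.8 / 5.7 |
| 120 (after planned 20% drop-out, nearer Week 24) | 30 / 60 / 90 | 0.9 / 1.8 / 2.7 | 1.5 / 3.0 / 4.5 |

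**3. The denominator.** For illustration, suppose cortisol suppression raises testing from 50% on vehicle to 75% on EP-104IAR, with 150 dosed per arm and 4 and 6 positives.

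- Out of those tested: 4/75 = 5.3% and 6/113 = 5.3%. The arms look the same.
- Out of those dosed: 4/150 = 2.7% and 6/150 = 4.0%.

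These counts show the mechanism; they are not a forecast.

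**4. The worst-result rule.** Visit 9 is Day 169 ± 7, so Days 162 to 176. Visit 9 and any later repeat both fall in the window from Day 149, so a Fail followed by a normal repeat is tabulated as Fail. A Week 12 Fail and its Visit 9 retest fall in different windows and are unaffected. Subjects tested at Visit 9 itself are mainly those already abnormal at Week 12, so an overridden repeat needs a Fail at Week 12, a Fail at Visit 9 and then a normal repeat. With no AI and n = 38, 75 or 113 tested at Week 12:

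- Independent errors: n × 0.03 × 0.03 × 0.97 = 0.03, 0.07 or 0.10 per arm.
- If half of false positives recur within a subject (assumed), the Screening exclusion lowers the first-test rate to (0.03 − 0.015)/0.97 = 0.0155. Then n × 0.0155 × 0.5 × 0.5 = 0.15, 0.29 or 0.44 per arm.

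**5. Week 24 positives from the unscheduled test.** Protocol 9.2.7 attaches its repeat to a test performed at Visit 9, not to the unscheduled test triggered by low Visit 9 cortisol. With 60 tested (50% of 120), false positives from that route are 60 × 0.0155 = 0.9 to 60 × 0.03 = 1.8 per arm. They share one cell with retests of Week 12 failures.

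**6. How many positives are real.** The false share of first-test positives is f(1 − p) / [0.95p + f(1 − p)]. At p = 2% (assumed) it is 61% for f = 0.03 and 44% for f = 0.0155. At p = 5% it is 38% and 24%. So roughly 39% to 76% of first-test positives would be true.

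**The case against.** The case for leaving the plan alone is strong in several places.

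- **The 1 in 20 clause drives nothing.** This stands. Glucocorticoid replacement is considered when an abnormal test comes with symptoms, the SRC example in Protocol 4.3 is confirmed symptomatic AI in more than one treated subject, and no hypothesis tests are planned on safety data. A reader might infer that the wrong rate would let a real excess pass as test error: six or more positives in 75 has probability 17% at 1 in 20 but 2.5% at 3%. The documents contain no such threshold, and the vehicle arm is the comparator.
- **The worst-result rule is conservative and affects almost nobody.** This also stands. A reader might infer that the Week 24 count is materially inflated by overridden repeats; step 4 puts them below one subject per arm, and the listings keep every test.
- **Repeat testing is not confined to Protocol 9.2.7.** Correct. Protocol 6.2 provides for confirmatory testing through the Medical Monitor, and 10.2.7 for further investigation of clinically significant abnormalities at the end of the study. It would be wrong to say that the other Week 24 positives cannot be repeated; those routes are discretionary.
- **Selective testing is open, and counts accompany percentages.** Partly stands. With 1:1 allocation the raw counts are roughly comparable, and the number tested can be worked back from any non-zero cell. The tabulated percentage still rests on the selected group.
- **Clinical AI is captured elsewhere.** AE tables by arm, including events of special interest, cover it, but they do not give test and retest results.

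**Conclusion.** The point holds as a minor one. The stated false-positive rate is inconsistent with the stated specificity: 3% (about 1 in 33) rather than 5%, conditional on 97% being the right figure. This changes no planned decision or analysis.

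The reporting gap is real but modest. The percentage positive is conditional on a cortisol trigger that treatment can affect, so it can mask an excess if EP-104IAR raises the testing rate. How far depends on testing rates that the documents do not give. The override of a normal confirmatory repeat is certain as a rule but small in effect: 0.03 to 0.44 subjects per arm under the assumptions shown.

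The primary endpoint, sample size and stopping rule are untouched. Nor do the documents support treating unrepeated positives as doubtful. On the assumed prevalences a substantial share would be true, and discounting them could hide real adrenal suppression.

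**What to change.** **Protocol 9.1.5.1.2.** Change the clause to about 1 in 33. If the source shows that the figures were transposed, correct the specificity to 95% (and the sensitivity to 97%) and leave 1 in 20.

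**SAP 3.8.4.2 and 4.4.** Keep the worst-result row as the conservative summary. Add, by arm:

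- the number tested at each time point, and positives as a percentage of the safety population, with a footnote that untested subjects are counted as not positive;
- the first-test result in each window;
- the number abnormal on both a test and its repeat;
- a Week 12 by Week 24 cross-tabulation, with a category for not tested.

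Report positives without a second test as *not repeated* rather than *unconfirmed*.

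**Cost.** One wording correction and a few table rows from data already collected. No extra ACTH test or visit is needed. The row for positives on both tests will hold very few subjects and should be read as a description only.

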9.1.5.1.3 Pregnancy Testing

Blood samples collected at Screening Visit 1a will be used to measure human chorionic gonadotropin (hCG) in female subjects of childbearing potential.

Urine samples collected at Visit 2 (pre-dose) and End-of-Study Visit (or Early Exit Visit) will be used for pregnancy testing in female subjects of childbearing potential.

Imaging Sub-Study

Urine samples for pregnancy testing will be acquired before each MRI for female subjects of childbearing potential. At Visit 2, the pregnancy test performed prior to the MRI does not need to be repeated prior to IMP administration.

